| Died on Study | xx (xx.x) | xx (xx.x) | xx (xx.x) |

Source: list SAS datasets used to create table
SAS X.Y

DDMONYYYYTHH:MM
program_name

Note to programmer: Only present overall sites.

Pacira Pharmaceuticals (Page X of Y) Protocol: 402-C-329
Table 14.3-4.1.2: Summary of Incidence of Treatment-Emergent Adverse Events (TEAEs) - Safety Analysis Set
Site: Overall

| System Organ Class Preferred Term | EXPAREL [N=XX] n (%) | Placebo [N=XX] n (%) | Total [N=XX] n (%) |
|--------------------------------------|-------------------------|-------------------------|-----------------------|
| Subjects with at least one TEAE | xx (xx.x) | xx (xx.x) | xx (xx.x) |
| SOC1 | xx (xx.x) | xx (xx.x) | xx (xx.x) |
| PT1.1 | xx (xx.x) | xx (xx.x) | xx (xx.x) |
| PT1.2 | xx (xx.x) | xx (xx.x) | xx (xx.x) |
| SOC2 | xx (xx.x) | xx (xx.x) | xx (xx.x) |
| PT2.1 | xx (xx.x) | xx (xx.x) | xx (xx.x) |
| PT2.2 | xx (xx.x) | xx (xx.x) | xx (xx.x) |
| ETC. | xx (xx.x) | xx (xx.x) | xx (xx.x) |

Adverse events coded using the Medical Dictionary for Regulatory Activities (MedDRA TBD).

Sorted by descending total incidence by system organ class and preferred term within system organ class.

Subjects experiencing the same TEAE more than once are counted only once at each summary level.

Source: list SAS datasets used to create table

DDMONYYYYTHH:MM

program_name

Note to programmer: Only present overall sites. Use mock-up Table 14.3-2.1.2 for the following tables:

Table 14.3-4.1.3: Summary of Incidence of Study Drug-Related Treatment-Emergent Adverse Events (TEAEs) - Safety Analysis Set

Table 14.3-4.1.4: Summary of Incidence of Treatment-Emergent Adverse Events (TEAEs) Leading to Study Withdrawal - Safety Analysis Set

Table 14.3-4.1.5: Summary of Incidence of Study Drug-Related Treatment-Emergent Adverse Events (TEAEs) Leading to Study Withdrawal - Safety Analysis Set

For related tables add the following footnote to the table:

Related TEAEs are those AEs indicated as 'possible', 'probable' or 'definite' related by the investigator on the AE CRF.

Pacira Pharmaceuticals

(Page X of Y)

Protocol: 402-C-329

Table 14.3-4.1.6: Summary of Incidence of Treatment-Emergent Adverse Events (TEAEs) by Severity - Safety
Analysis Set
Site: Overall

| System Organ Class Preferred Term | Severity | EXPAREL [N=XX] n (%) | Placebo [N=XX] n (%) | Total [N=XX] n (%) |
|--------------------------------------|----------|-------------------------|-------------------------|-----------------------|
| Subjects with at least one TEAE | | | | |
| | Mild | xx (xx.x) | xx (xx.x) | xx (xx.x) |
| | Moderate | xx (xx.x) | xx (xx.x) | xx (xx.x) |
| | Severe | xx (xx.x) | xx (xx.x) | xx (xx.x) |
| SOC1 | | | | |
| | Mild | xx (xx.x) | xx (xx.x) | xx (xx.x) |
| | Moderate | xx (xx.x) | xx (xx.x) | xx (xx.x) |
| | Severe | xx (xx.x) | xx (xx.x) | xx (xx.x) |
| PT1.1 | | | | |
| | Mild | xx (xx.x) | xx (xx.x) | xx (xx.x) |
| | Moderate | xx (xx.x) | xx (xx.x) | xx (xx.x) |
| | Severe | xx (xx.x) | xx (xx.x) | xx (xx.x) |
| PT1.2 | | | | |
| | Mild | xx (xx.x) | xx (xx.x) | xx (xx.x) |
| | Moderate | xx (xx.x) | xx (xx.x) | xx (xx.x) |
| SOC2 | | | | |
| | Severe | xx (xx.x) | xx (xx.x) | xx (xx.x) |
| | | | | |
| | Mild | xx (xx.x) | xx (xx.x) | xx (xx.x) |
| | Moderate | xx (xx.x) | xx (xx.x) | xx (xx.x) |
| | Severe | xx (xx.x) | xx (xx.x) | xx (xx.x) |
| PT2.1 | | | | |
| | Mild | xx (xx.x) | xx (xx.x) | xx (xx.x) |
| | Moderate | xx (xx.x) | xx (xx.x) | xx (xx.x) |
| | Severe | xx (xx.x) | xx (xx.x) | xx (xx.x) |
| ETC. | | | | |

Adverse events coded using the Medical Dictionary for Regulatory Activities (MedDRA TBD).

Sorted by descending total incidence by system organ class and preferred term within system organ class.

Subjects experiencing the same TEAE more than once are counted only once at each summary level.

Source: list SAS datasets used to create table

DDMONYYYYTHH:MM

program_name

SAS X.Y

Pacira Pharmaceuticals

(Page X of Y)

Protocol: 402-C-329

Table 14.3-4.1.7: Summary of Incidence of Treatment-Emergent Adverse Events (TEAEs) by Relationship to Study Drug - Safety Analysis Set

Site: Overall

| System Organ Class Preferred Term | Severity | EXPAREL [N=XX] n (%) | Placebo [N=XX] n (%) | Total [N=XX] n (%) |
|--------------------------------------|----------|-------------------------|-------------------------|-----------------------|
| Subjects with at least one TEAE | | | | |
| | Unlikely | xx (xx.x) | xx (xx.x) | xx (xx.x) |
| | Possible | xx (xx.x) | xx (xx.x) | xx (xx.x) |
| | Probable | xx (xx.x) | xx (xx.x) | xx (xx.x) |
| | Definite | xx (xx.x) | xx (xx.x) | xx (xx.x) |
| SOC1 | | | | |
| | Unlikely | xx (xx.x) | xx (xx.x) | xx (xx.x) |
| | Possible | xx (xx.x) | xx (xx.x) | xx (xx.x) |
| | Probable | xx (xx.x) | xx (xx.x) | xx (xx.x) |
| | Definite | xx (xx.x) | xx (xx.x) | xx (xx.x) |
| PT1.1 | | | | |
| | Unlikely | xx (xx.x) | xx (xx.x) | xx (xx.x) |
| | Possible | xx (xx.x) | xx (xx.x) | xx (xx.x) |
| | Probable | xx (xx.x) | xx (xx.x) | xx (xx.x) |
| | Definite | xx (xx.x) | xx (xx.x) | xx (xx.x) |
| PT1.2 | | | | |
| | Unlikely | xx (xx.x) | xx (xx.x) | xx (xx.x) |
| | Possible | xx (xx.x) | xx (xx.x) | xx (xx.x) |
| | Probable | xx (xx.x) | xx (xx.x) | xx (xx.x) |
| | Definite | xx (xx.x) | xx (xx.x) | xx (xx.x) |
| SOC2 | | | | |
| | Unlikely | xx (xx.x) | xx (xx.x) | xx (xx.x) |
| | Possible | xx (xx.x) | xx (xx.x) | xx (xx.x) |
| | Probable | xx (xx.x) | xx (xx.x) | xx (xx.x) |
| | Definite | xx (xx.x) | xx (xx.x) | xx (xx.x) |

ETC.

Adverse events coded using the Medical Dictionary for Regulatory Activities (MedDRA TBD).

Sorted by descending total incidence by system organ class and preferred term within system organ class.

Subjects experiencing the same TEAE more than once are counted only once at each summary level.

Source: list SAS datasets used to create table

SAS X.Y

DDMONYYYYTHH:MM
program_name

Document No. < >

CONFIDENTIAL

83 of 125

12 November 2015

Note to programmer: Only present overall sites.

Note to programmer: Only present overall sites. Use templates 14.3.1-1 through 14.3.1-7 respectively for the following tables:

Table 14.3-4.2.1: Overview of Serious Treatment-Emergent Adverse Events (TEAEs) - Safety Analysis Set

Table 14.3-4.2.2: Summary of Incidence of Serious Treatment-Emergent Adverse Events (TEAEs) - Safety Analysis Set

Table 14.3-4.2.3: Summary of Incidence of Study Drug-Related Serious Treatment-Emergent Adverse Events (TEAEs) - Safety Analysis Set

Table 14.3-4.2.4: Summary of Incidence of Serious Treatment-Emergent Adverse Events (TEAEs) Leading to Study Withdrawal - Safety Analysis Set

Table 14.3-4.2.5: Summary of Incidence of Study Drug-Related Serious Treatment-Emergent Adverse Events (TEAEs) Leading to Study Withdrawal - Safety Analysis Set

Table 14.3-4.2.6: Summary of Incidence of Serious Treatment-Emergent Adverse Events (TEAEs) Resulting in Death - Safety Analysis Set

Table 14.3-4.2.7: Summary of Incidence of Study Drug-Related Serious Treatment-Emergent Adverse Events (TEAEs) Resulting in Death - Safety Analysis Set

| Pacira Pharmaceuticals | | (Page X of Y) | | Protocol: 402-C-329 | |
|---|----------------|-------------------------|-------------------------|-----------------------|--|
| Table 14.3-5.1: Summary of Incidence of Prior Medications - Safety Analysis Set | | | | | |
| Site: Overall | | | | | |
| Anatomical Therapeutic Class (ATC) | Preferred Name | EXPAREL [N=XX] n (%) | Placebo [N=XX] n (%) | Total [N=XX] n (%) | |
| Subjects taking at least one medication | | xx (xx.x) | xx (xx.x) | xx (xx.x) | |
| ATC1 | | xx (xx.x) | xx (xx.x) | xx (xx.x) | |
| PN1.1 | | xx (xx.x) | xx (xx.x) | xx (xx.x) | |
| PN1.2 | | xx (xx.x) | xx (xx.x) | xx (xx.x) | |
| ATC2 | | xx (xx.x) | xx (xx.x) | xx (xx.x) | |
| PN2.1 | | xx (xx.x) | xx (xx.x) | xx (xx.x) | |
| PN2.2 | | xx (xx.x) | xx (xx.x) | xx (xx.x) | |
| ETC. | | xx (xx.x) | xx (xx.x) | xx (xx.x) | |

Medications are coded using World Health Organization Drug Dictionary (WHO-DD) March 2015.

Sorted by descending total incidence by ATC and preferred name within ATC.

Prior medications are those stopped before end of surgery.

Subjects using the same prior medication more than once are counted only once at each summary level.

Source: list SAS datasets used to create table

DDMONYYYYTHH:MM

SAS X.Y

program_name

Note to programmer: Only present overall sites. Use this template for the following tables:

Table 14.3-5.2: Incidence of Concomitant Medications - Safety Analysis Set.

On these tables change the footnote 'Prior medications are those stopped before end of surgery' to read 'Concomitant medications are those taken between the end of surgery and discharge from study' on Table 14.3-5.2.

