9.2. Discussion of Study Design

EXPAREL is approved for infiltration into a surgical site. This multicenter, randomized, double-blind, placebo-controlled study is designed to evaluate the safety, efficacy, and pharmacokinetics of local administration of EXPAREL for prolonged postsurgical analgesia in subjects undergoing third molar extraction. The double blind study design is intended to avoid potential bias resulting from subject or Investigator knowledge of the assigned treatment.

Third molar extraction is a frequently performed surgical procedure that causes considerable postsurgical pain, particularly following removal of impacted lower mandibular third molars. Standard postoperative analgesia following third molar extraction often includes combination opioid analgesics. In this study, all subjects will receive PO oxycodone, as needed, to control breakthrough postsurgical pain.

Neurological and cardiac assessments will be conducted to rule out bupivacaine toxicity related to high plasma exposure.

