7.7.2. Electrocardiograms

Investigator Read

Investigator's interpretation of ECGs will be tabulated by treatment presenting the number and percentage of subjects in all of the reported interpretations.

Central Read

Electrocardiogram intervals (RR, PR, QRS, QT, QTcB, and QTcF) and heart rate will be summarized by treatment at each assessment timepoint. Electrocardiogram interval derivations and morphological analysis will be done by a central reader.

Summaries will present both actual and change-from-baseline results for all ECG parameters. Baseline statistics will be presented at each assessment timepoint for those subjects reporting data at that timepoint. The summary will highlight the timepoint closest the median PK Tmax observed during the study.

The ECG data will be assessed for potentially clinically meaningful values (see [Table 4](#)). The number and percentage of subjects satisfying the potentially clinically significant abnormal criteria at any time during the study and at each assessment timepoint will be tabulated. The table will present the number and percentage of subjects meeting the individual criteria (critical value, critical change) as well as the composite criteria (critical value and critical change). To satisfy the composite criteria the subject must satisfy both within the same ECG read.

Table 4: Criteria for Potentially Clinically Meaningful ECG Results

| ECG Parameter | Unit | Critical Value | Critical Change ¹ |
|---------------|------|----------------|------------------------------|
|---------------|------|----------------|------------------------------|

| | | | |
|--------------|-------------|-----------------------|--|
| Heart rate | Bpm | > 100 < 50 | Increase of at least 25 Decrease of at least 25 |
| PR Interval | millisecond | > 200 | Increase of at least 25 |
| QRS Interval | millisecond | > 100 | Increase of at least 25 |
| QT Interval | millisecond | > 500 | Baseline \leq 500 |
| QTcF | millisecond | > 500 >480 >450 | Baseline \leq 500 Baseline \leq 480 Baseline \leq 450 >30-60 >60 |
| QTcB | millisecond | > 500 >480 >450 | Baseline \leq 500 Baseline \leq 480 Baseline \leq 450 >30-60 >60 |

¹Change criteria not applicable at baseline or screening.

Tabulations of the number and percent of subjects with each of the ECG morphologies identified by the central reader will be presented by treatment at each assessment timepoint.

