| | | Yes | n (%) | XX (XX.X) | XX (XX.X) | XX (XX.X) |
| At anytime after baseline | | | | | | |
| | Numbness of lips, tongue or mouth | No | n (%) | XX (XX.X) | XX (XX.X) | XX (XX.X) |
| | | Yes | n (%) | XX (XX.X) | XX (XX.X) | XX (XX.X) |
| Metallic taste | | | | | | |
| | | No | n (%) | XX (XX.X) | XX (XX.X) | XX (XX.X) |
| | | Yes | n (%) | XX (XX.X) | XX (XX.X) | XX (XX.X) |
| Hearing problems | | | | | | |
| | | No | n (%) | XX (XX.X) | XX (XX.X) | XX (XX.X) |
| | | Yes | n (%) | XX (XX.X) | XX (XX.X) | XX (XX.X) |
| Vision problems | | | | | | |
| | | No | n (%) | XX (XX.X) | XX (XX.X) | XX (XX.X) |
| | | Yes | n (%) | XX (XX.X) | XX (XX.X) | XX (XX.X) |
| Muscle twitching | | | | | | |
| | | No | n (%) | XX (XX.X) | XX (XX.X) | XX (XX.X) |
| | | Yes | n (%) | XX (XX.X) | XX (XX.X) | XX (XX.X) |

Source: list SAS datasets used to create table

SAS X.Y

DDMONYYYYTHH:MM

program_name

Note to programmer: Only present overall sites. Timepoints to appear on this table are, in order of appearance, Baseline (prior to surgery), At anytime after baseline, 15 and 30 minutes and 1, 2, 4, 8, 12, 18, 24, 30, 36, 42, 48, 54, 60, 66, 72, 84 and 96 hours. Do not split a timepoint across pages. For the timepoint 'anytime after baseline' if there is at least one 'yes' at any timepoint but baseline, the subject will be a 'yes'.

Pacira Pharmaceuticals (Page X of Y) Protocol: 402-C-329
Table 14.3-2.1 Summary of Electrocardiogram Parameters - Central Read - Safety Analysis Set
Site: Overall

| ECG Parameter | Timepoint | Value | Statistic | EXPAREL [N=XX] | Placebo [N=XX] | Total [N=XXX] |
|------------------|-----------------------------|----------------------|--------------------|-------------------|-------------------|------------------|
| Heart Rate (bpm) | | | | | | |
| | Baseline | Actual | n | xx | xx | xx |
| | | | Mean | xx.x | xx.x | xx.x |
| | | | Standard Deviation | x.xx | x.xx | x.xx |
| | | | Minimum | xx | xx | xx |
| | | | Median | xx.x | xx.x | xx.x |
| | | | Maximum | xx | xx | xx |
| | At Median Tmax (XX Hour) | Baseline Actual[1] | n | xx | xx | xx |
| | | | Mean | xx.x | xx.x | xx.x |
| | | | Standard Deviation | x.xx | x.xx | x.xx |
| | | | Minimum | xx | xx | xx |
| | | | Median | xx.x | xx.x | xx.x |
| | | | Maximum | xx | xx | xx |
| | | Actual | n | xx | xx | xx |
| | | | Mean | xx.x | xx.x | xx.x |
| | | | Standard Deviation | x.xx | x.xx | x.xx |
| | | | Minimum | xx | xx | xx |
| | | | Median | xx.x | xx.x | xx.x |

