| | | Decrease >= 25 | n (%) | xx (xx.x%) | xx (xx.x%) | xx (xx.x%) |
| | | < 50 & Decrease >= 25 | n (%) | xx (xx.x%) | xx (xx.x%) | xx (xx.x%) |
| | | > 100 | n (%) | xx (xx.x%) | xx (xx.x%) | xx (xx.x%) |
| | | Increase >= 25 | n (%) | xx (xx.x%) | xx (xx.x%) | xx (xx.x%) |
| | | > 100 & Increase >= 25 | n (%) | xx (xx.x%) | xx (xx.x%) | xx (xx.x%) |
| | 15 minutes | < 50 | n (%) | xx (xx.x%) | xx (xx.x%) | xx (xx.x%) |
| | | Decrease >= 25 | n (%) | xx (xx.x%) | xx (xx.x%) | xx (xx.x%) |
| | | < 50 & Decrease >= 25 | n (%) | xx (xx.x%) | xx (xx.x%) | xx (xx.x%) |
| | | > 100 | n (%) | xx (xx.x%) | xx (xx.x%) | xx (xx.x%) |
| | | Increase >= 25 | n (%) | xx (xx.x%) | xx (xx.x%) | xx (xx.x%) |
| | | > 100 & Increase >= 25 | n (%) | xx (xx.x%) | xx (xx.x%) | xx (xx.x%) |

Source: list SAS datasets used to create table
SAS X.Y

DDMONYYYYTHH:MM
program_name

Document No. < >
CONFIDENTIAL

Note to programmer: Only present overall sites. Electrocardiogram intervals are 'Heart Rate (bpm)', 'PR Interval (msec)', 'QRS Interval (msec)', 'QT Interval (msec)', 'QTcF Interval (msec)', 'QTcB Interval (msec).' Timepoints to appear on this table are, in order of appearance, Baseline, Any time after Baseline, At Median Tmax (X hour), At Subjects' Tmax, 15 and 30 minutes and 1, 2, 4, 8, 12, 18, 24, 30, 36, 42, 48, 54, 60, 66, 72, 84 and 96 hours. Don't split timepoint across pages. Note that the At Median Tmax (X hour) timepoint will be a duplicate of X hour summary.

| Pacira Pharmaceuticals | | (Page X of Y) | | Protocol: 402-C-329 | |
|--|------------------------------------|---------------|-------------------|---------------------|------------------|
| Table 14.3-2.3: Tabulation Electrocardiogram Morphology Results - Central Read - Safety Analysis Set | | | | | |
| Time Point | Morphology | Statistic | EXPAREL [N=XX] | Placebo [N=XX] | Total [N=XXX] |
| Any Time After Baseline | | | | | |
| | No Findings | n (%) | xx (xx.x%) | xx (xx.x%) | xx (xx.x%) |
| | At Least One Finding | n (%) | xx (xx.x%) | xx (xx.x%) | xx (xx.x%) |
| | Abnormal U Wave | n (%) | xx (xx.x%) | xx (xx.x%) | xx (xx.x%) |
| | ST Segment Elevation | n (%) | xx (xx.x%) | xx (xx.x%) | xx (xx.x%) |
| | ST Segment Depression | n (%) | xx (xx.x%) | xx (xx.x%) | xx (xx.x%) |
| | T Wave Inversion | n (%) | xx (xx.x%) | xx (xx.x%) | xx (xx.x%) |
| | Second or Third Degree Heart Block | n (%) | xx (xx.x%) | xx (xx.x%) | xx (xx.x%) |
| | LBBB | n (%) | xx (xx.x%) | xx (xx.x%) | xx (xx.x%) |

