| | RBBB | n (%) | xx (xx.x%) | xx (xx.x%) | xx (xx.x%) |
| | Atrial Fibrillation | n (%) | xx (xx.x%) | xx (xx.x%) | xx (xx.x%) |
| | Atrial Flutter | n (%) | xx (xx.x%) | xx (xx.x%) | xx (xx.x%) |
| | MI | n (%) | xx (xx.x%) | xx (xx.x%) | xx (xx.x%) |
| Baseline | | | | | |
| | No Findings | n (%) | xx (xx.x%) | xx (xx.x%) | xx (xx.x%) |
| | At Least One Finding | n (%) | xx (xx.x%) | xx (xx.x%) | xx (xx.x%) |
| | Abnormal U Wave | n (%) | xx (xx.x%) | xx (xx.x%) | xx (xx.x%) |
| | ST Segment Elevation | n (%) | xx (xx.x%) | xx (xx.x%) | xx (xx.x%) |
| | ST Segment Depression | n (%) | xx (xx.x%) | xx (xx.x%) | xx (xx.x%) |
| | T Wave Inversion | n (%) | xx (xx.x%) | xx (xx.x%) | xx (xx.x%) |
| | Second or Third Degree Heart Block | n (%) | xx (xx.x%) | xx (xx.x%) | xx (xx.x%) |
| | LBBB | n (%) | xx (xx.x%) | xx (xx.x%) | xx (xx.x%) |
| | RBBB | n (%) | xx (xx.x%) | xx (xx.x%) | xx (xx.x%) |
| | Atrial Fibrillation | n (%) | xx (xx.x%) | xx (xx.x%) | xx (xx.x%) |
| | Atrial Flutter | n (%) | xx (xx.x%) | xx (xx.x%) | xx (xx.x%) |
| | MI | n (%) | xx (xx.x%) | xx (xx.x%) | xx (xx.x%) |

Source: list SAS datasets used to create table
SAS X.Y

DDMONYYYYTHH:MM
program_name

Note to programmer: Only present overall sites. Electrocardiogram morphology list presented in mock-up may not be complete (or may contain items not found during study), the list should only present those morphologies found during the study. Timepoints to appear on this table are, in order of appearance, At Any Time After Baseline, Baseline, X hour (Tmax), 15 and 30 minutes and 1, 2, 4, 8, 12, 18, 24, 30, 36, 42, 48,

Document No. < >

CONFIDENTIAL

54, 60, 66, 72, 84 and 96 hours. Don't split timepoint across pages. Note that the X hour (Tmax) timepoint will be a duplicate of X hour summary.

| Pacira Pharmaceuticals | | (Page X of Y) | | Protocol: 402-C-329 | |
|---|--------------------------------------|---------------|-------------------|---------------------|------------------|
| Table 14.3-2.4: Tabulation Electrocardiogram Interpretation - Investigator Read - Safety Analysis Set | | | | | |
| Time Point | Interpretation | Statistic | EXPAREL [N=XX] | Placebo [N=XX] | Total [N=XXX] |
| Any Time After Baseline | | | | | |
| | Normal | n (%) | xx (xx.x%) | xx (xx.x%) | xx (xx.x%) |
| | Abnormal, Not clinically significant | n (%) | xx (xx.x%) | xx (xx.x%) | xx (xx.x%) |
| | Abnormal, Clinically significant | n (%) | xx (xx.x%) | xx (xx.x%) | xx (xx.x%) |

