| Baseline | Normal | n (%) | xx (xx.x%) | xx (xx.x%) | xx (xx.x%) |
| | Abnormal, Not clinically significant | n (%) | xx (xx.x%) | xx (xx.x%) | xx (xx.x%) |
| | Abnormal, Clinically significant | n (%) | xx (xx.x%) | xx (xx.x%) | xx (xx.x%) |

Source: list SAS datasets used to create table
SAS X.Y

DDMONYYYYTHH:MM
program_name

Note to programmer: Only present overall sites. Timepoints to appear on this table are, in order of appearance, At Any Time After Baseline, Baseline, X hour (Tmax), 15 and 30 minutes and 1, 2, 4, 8, 12, 18, 24, 30, 36, 42, 48, 54, 60, 66, 72, 84 and 96 hours. Don't split timepoint across pages. Note that the X hour (Tmax) timepoint will be a duplicate of X hour summary.

Pacira Pharmaceuticals
Table 14.3-3.1: Summary of Vital Signs - Safety Analysis Set
Site: Overall

Protocol: 402-C-329

| Vital Sign | Timepoint | Value | Statistic | EXPAREL [N=XX] | Placebo [N=XX] | Total [N=XXX] |
|--------------------------|-----------|----------------------|--------------------|-------------------|-------------------|------------------|
| Resting Heart Rate (bpm) | | | | | | |
| | Baseline | Actual | n | xx | xx | xx |
| | | | Mean | xx.x | xx.x | xx.x |
| | | | Standard Deviation | x.xx | x.xx | x.xx |
| | | | Minimum | xx | xx | xx |
| | | | Median | xx.x | xx.x | xx.x |
| | | | Maximum | xx | xx | xx |
| | 1 hour | Baseline Actual[1] | n | xx | xx | xx |
| | | | Mean | xx.x | xx.x | xx.x |
| | | | Standard Deviation | x.xx | x.xx | x.xx |
| | | | Minimum | xx | xx | xx |
| | | | Median | xx.x | xx.x | xx.x |
| | | | Maximum | xx | xx | xx |
| | | Actual | n | xx | xx | xx |
| | | | Mean | xx.x | xx.x | xx.x |
| | | | Standard Deviation | x.xx | x.xx | x.xx |
| | | | Minimum | xx | xx | xx |
| | | | Median | xx.x | xx.x | xx.x |
| | | | Maximum | xx | xx | xx |
| | | Change from Baseline | n | xx | xx | xx |
| | | | Mean | xx.x | xx.x | xx.x |
| | | | Standard Deviation | x.xx | x.xx | x.xx |
| | | | Minimum | xx | xx | xx |
| | | | Median | xx.x | xx.x | xx.x |
| | | | Maximum | xx | xx | xx |

[1] Baseline (prior to surgery) for subjects with data at the timepoint.

Source: list SAS datasets used to create table

SAS X.Y

DDMONYYYYTHH:MM
program_name

Note to programmer: Only present overall sites. Vital signs are 'Resting Heart Rate (bpm)', 'Systolic Blood Pressure (mmHg)' and 'Diastolic Blood Pressure (mmHg)'. Timepoints to appear on this table are Baseline, 1, 2 and 4 hour. Don't split timepoint across pages.

Document No. < >

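### The any-time rows of the ECG morphology and investigator-read tables do not separate new findings from pre-existing ones, and in the investigator table a subject may count as both Normal and Abnormal

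*SAP*

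**What the plan says.** SAP 7.7.2 treats the two ECG reads separately. The investigator's interpretation is tabulated by treatment, "presenting the number and percentage of subjects in all of the reported interpretations". For the central read, the rule is "Tabulations of the number and percent of subjects with each of the ECG morphologies identified by the central reader will be presented by treatment", and this is repeated for every scheduled time. Neither sentence refers to the subject's baseline ECG, and neither says how a subject's many post-dose ECGs collapse into a single row.

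The shells in SAP 11.1 give both tables the same order of blocks: "Timepoints to appear on this table are, in order of appearance, At Any Time After Baseline, Baseline, X hour (Tmax", then every scheduled time to 96 hours. Table 14.3-2.3 has a No Findings row, an "At Least One Finding" row and one row per morphology. Table 14.3-2.4 has Normal, "Abnormal, Not clinically significant" and the clinically significant counterpart. Baseline is a separate block of arm totals. No planned table crosses a subject's baseline read with later reads.

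Elsewhere the plan does set such rules. The neurological table has a collapse rule: "if there is at least one 'yes' at any timepoint but baseline, the subject will be a 'yes". Interval and rate outliers have change-from-baseline criteria, and "To satisfy the composite criteria the subject must satisfy both within the same ECG read". Adverse event summaries are restricted to treatment-emergent events (SAP 7.7.4).

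**The concern.** Protocol 9.2 gives the purpose of these recordings: "Neurological and cardiac assessments will be conducted to rule out bupivacaine toxicity related to high plasma exposure". Protocol 9.1 names heart block among the cardiac events of interest. For that purpose the useful count is the number of subjects who acquire an abnormality after dosing.

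As written, the any-time block also counts subjects whose abnormality was already on the pre-surgery ECG. They add roughly equal numbers to both arms, which shrinks the contrast and adds noise. In Table 14.3-2.4, a subject with many normal ECGs and one abnormal ECG can appear in both rows. Two programmers could reasonably build different any-time blocks from the same text.

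**Working it through.** **Number of ECGs.** Protocol 12.5 schedules post-dose ECGs at 15 and 30 minutes and at 1, 2, 4, 8, 12, 18, 24, 30, 36, 42, 48, 54, 60, 66, 72, 84 and 96 hours. That is 19, and Day 10 makes 20. Planned arms are 100 EXPAREL and 75 placebo (Protocol 9.1). The documents give no ECG finding rates, so every rate below is an assumption.

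**Dilution.** Let b be the baseline prevalence, the same in both arms and persisting after dosing. Let p be the new-onset rate among subjects free of the finding at baseline. The any-time rate is b + (1 − b)p, so the difference between arms is (1 − b)(pE − pP). With pE = 10% and pP = 2%:

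| b | EXPAREL | Placebo | Difference (points) | Ratio |
|---|---|---|---|---|
| 0% | 10.0% | 2.0% | 8.0 | 5.0 |
| 1% | 10.9% | 2.98% | 7.92 | 3.66 |
| 5% | 14.5% | 6.9% | 7.6 | 2.10 |
| 10% | 19.0% | 11.8% | 7.2 | 1.61 |
| 20% | 28.0% | 21.6% | 6.4 | 1.30 |
| 30% | 37.0% | 31.4% | 5.6 | 1.18 |

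A new-onset line would show 10% against 2% at every b. For precision, at b = 20%:

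- Any-time row: SE = √(0.28×0.72/100 + 0.216×0.784/75) = 6.5 points on a difference of 6.4.
- New-onset line (80 and 60 subjects at risk): SE = √(0.10×0.90/80 + 0.02×0.98/60) = 3.8 points on a difference of 8.0.

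At b = 1% the same formulas give 7.92 (SE 3.7) against 8.0 (SE 3.4), which is little loss.

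**Can the Baseline block recover new onset?** Yes, if every subject with the finding at baseline shows it on at least one post-dose ECG. New onset is then (any-time − b)/(1 − b). At b = 20% this gives (28.0 − 20)/80 = 10% and (21.6 − 20)/80 = 2%, the assumed rates exactly.

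If baseline findings can disappear, it is not recoverable. Take an arm of 100 with 20 T-wave inversions at baseline. Suppose 10 are never seen again and 10 other subjects acquire one. The any-time count is 20 − 10 + 10 = 20, the same as if nobody had a new finding. In general, with B at baseline and A any-time out of N, the number of new cases can lie anywhere from max(0, A − B) to min(A, N − B); here that is 0 to 20.

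**Overlap in Table 14.3-2.4.** Suppose each ECG has an independent chance q of an abnormal read. Over the 19 ECGs to 96 hours, the share of subjects with both a normal and an abnormal read is 1 − (1 − q)^19 − q^19. This is 17.4% at q = 1%, 31.9% at 2% and 62.3% at 5%. The share with at least one normal read is 1 − q^19, essentially 100%. Reads within a person are likely to be correlated, which would lower the overlap figures. The Normal row would still be close to full in both arms.

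**The case against.** The strongest reply is that little is lost. The same tables show Baseline and every time to 96 hours by arm, and randomization should balance baseline findings. Conduction is also covered by PR and QRS: change from baseline in Table 14.3-2.1, and criteria in Table 14.3-2.2 that include an increase of at least 25 ms. An ECG abnormality recorded as an adverse event enters the treatment-emergent tables, which require onset after dosing. Listings 16.2-14.1 and 16.2-14.2.1 run from screening and time 0. High baseline prevalence is unlikely for rows such as second- or third-degree block or atrial fibrillation, because exclusion criterion 6 covers significant cardiovascular disease including rhythm disturbance, subject to the Investigator's judgement. No test on ECG data is planned.

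Most of this stands, and it rules out three stronger readings.

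- A reader might infer that a new abnormality on EXPAREL is buried. It is not: every abnormal post-baseline read stays in its abnormal row.
- A reader might infer that new onset can never be recovered. It can, when baseline findings are seen again after dosing.
- A reader might extend the double counting to Table 14.3-2.3. There, No Findings set against "At Least One Finding" reads as mutually exclusive.

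Even in Table 14.3-2.4 the overlap is permitted rather than prescribed, since the SAP wording could mean only that every category is displayed.

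The gap that remains is narrower. ST-T changes have no interval counterpart and are the kind of finding that can come and go. Adverse event entry depends on the Investigator recording the finding. Reconstruction from listings means about 175 × 21 = 3,675 baseline and post-dose lines per read.

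**Conclusion.** The point holds as a minor reporting weakness. The any-time block mixes new and pre-existing findings, and no shift from baseline is planned, so a drug-related excess is diluted. The ratio suffers most (5.0 to 1.61 at 10% prevalence, 1.30 at 20%). The difference shrinks only by the factor 1 − b, and for findings rare at baseline it is nearly intact. Arm totals recover new onset only if baseline findings are seen again after dosing.

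Separately, the wording for Table 14.3-2.4 permits a subject to be counted as both Normal and Abnormal, which makes the Normal row uninformative; the abnormal rows remain complete.

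The sizes rest on assumed onset rates, equal and persistent baseline prevalence in both arms and, for the overlap, independent reads. The tables are descriptive, so no planned test or efficacy conclusion is affected. The case for acting is that a more informative count is available from data already collected, and that it matches how the plan treats intervals and adverse events.

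**What to change.** In SAP 7.7.2 and the two shells:

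- **Table 14.3-2.4:** in the any-time block, classify each subject once by the worst post-baseline interpretation, and cross-tabulate that against the baseline interpretation by arm.
- **Table 14.3-2.3:** keep the present count and add, for each morphology, a new-since-baseline line with subjects free of that finding at baseline as the denominator.
- **Both:** state which ECGs the any-time block spans. The shells list times only to 96 hours, although a Day 10 ECG is scheduled.

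The cost is a few sentences of text and a little programming, with no new data. The price in the output is a denominator that varies by morphology and is smaller than the full safety set.
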